## 5. TREATMENT OF SUBJECTS

### 5.1 Investigational product/treatment

The investigational product that will be used in this study is the Healthy Mind Virtual Reality device.[7] VR distraction therapy device aimed to reduce pain and anxiety in hospitalized patients. This is a CE mark class I medical device. The device contains software which puts patients in immersive virtual experiences to distract them from reality using advanced psychological principles like medical hypnosis. The software also contains breathing exercises which are essential in the postoperative setting in cardiac surgery.

By using the brain's cognitive and affective capacities, pain pathways are modulated through combined visual and auditory stimulations, attention diversion and relaxation. With the use of virtual reality the patient is transported into a designed 3D environment to journey through natural experiences of choice. This device is designed to eventually be a drug-free therapeutic tool that facilitates the work of caregivers, transform conventional clinical pathways of patients and improve their recovery.

## 6. INVESTIGATIONAL PRODUCT

### 6.1 Name and description of investigational product

Our investigational product is the Healthy Mind Virtual Reality device. [7] This product is intended to be a VR distraction therapy device to reduce pain and anxiety by usage of software which gives patients an immersive experience in a calming VR environment with integrated breathing exercises.

### 6.2 Summary of findings from non-clinical studies

This device is developed with evidence based efficiency of VR treatment modalities in reducing pain and anxiety throughout different medical fields. See the literature review of the Healthy Mind VR device for an extensive description of these previous studies.[9]

At the current moment there are no completed studies in which the Healthy Mind VR device is used as investigational product. However, there are several ongoing clinical trials in France and Switzerland.

### 6.3 Summary of known and potential risks and benefits

#### Potential risks:

Some patients may present a non-adherence to the VR relaxation technique, resulting in discomfort and/or nausea and dizziness. The limitations of VR can be related to lacking physical adaptation which can potentially result in cyber-sickness.

The brain uses three sources of data to inform the body about its position and movements: the inner ear, muscles, and eyes. Once the head mounted display is on your head, the eyes indicate that you are in a different environment, but the inner ear and muscles say that this is not the case: this inconsistency of sensory information usually translates into temporary symptoms such eye fatigue, disorientation (dizziness, imbalance) and nausea. However, the Healthy Mind software was created specifically for patients with reduced mobility (lying or sitting) and optimized to minimize adverse effects such as nausea. For example, the user is not in constant movement in the virtual environment. Users remain static and are being teleported to new areas of the environment. This way, the gap between the inner ear and the virtual world is minimized. Furthermore, participants in this study will be excluded from further participation as soon as the above mentioned symptoms are noticed.

Potential benefits:

The VR technique of Healthy Mind uses the brain's cognitive and affective capacities to modulate pain pathways through combined visual and auditory stimulations, attention diversion and relaxation. The software on this device puts patients in immersive experiences in VR to distract them from reality. The software also integrates breathing exercises which are essential in the postoperative setting in cardiac surgery for lung recovery.

Altogether, the potential benefits of these elements would be pain reduction, anxiety reduction, improved lung recovery and faster general post-operative recovery.

**6.4 Description and justification of route of administration and dosage**

Since this a non-pharmaceutical investigational product, there is no evidence based description of dosage. However, usage for 2-3 sessions each day is maintained as the standard use in various clinics with similar VR therapeutic devices. Administration in this case is usage of a head-mounted device with earphones bringing the participants in a virtual reality environment for a session of 20 minutes.

## **7. METHODS**

### **7.1 Study parameters**

#### **7.1.1 Main study parameters**

The main study parameters are:

- Numeric Rating Scale (NRS) to assess the effect of pain on mobility
- Quality of Recovery-15 (QoR-15) questionnaire
- State-Trait Anxiety Inventory-6 (STAI-6) questionnaire
- Assessment of analgesic use

#### **7.1.2 Secondary study parameters**

The secondary study parameters are:

- Functional Ambulation Categories Score

### **7.2 Randomisation, blinding and treatment allocation**

For randomisation, we use a simple random allocation approach. This randomization sequence will be prepared in SPSS 26.0 (SPSS Inc, Chicago, IL) for Windows. This randomization will be performed postoperatively by the research team, in case of an uncomplicated procedure, directly after the patient returns to the clinical ward after surgery. Blinding however, is not possible in this study as usage of the medical device is clear.

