### **7.3 Study procedures**

The study will consist of 100 participants who have undergone an uncomplicated surgical CABG procedure.

The intervention group includes 50 patients using a VR distraction therapy device with 3D interactive nature environments in the post-operative stage for pain and anxiety management. The control group includes 50 patients who will be treated with conventional post-operative pain and anxiety management.

The intervention group will test-use the VR distraction therapy device on the day of clinical admission prior to surgery and use it therapeutic at day 1, 2 and 3 after surgery on the general ward.

Daily usage of the VR distraction therapy device consists of two sessions each day (morning and afternoon) with a duration of 20 minutes per session. The specific virtual environment for each session will be selected freely by the participants.

Outcomes will be measured daily, at the end of each session, which is done 1) after the doctor's ward visit in the morning and 2) after the shift change of the nurse team.

Outcomes will be measured at the same aforementioned moments in the control group.

Outcomes will be measured by using the Numeric Rating Scale (NRS) to assess the effect of pain on mobility, Quality of Recovery-15 questionnaire, State-Trait Anxiety Inventory-6 questionnaire and assessment of analgesic use.

At follow-up, participants will be called to gather one-time QoR-15 and STAI-6 questionnaire data 6 weeks after the surgery.

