#### **Numeric Rating Scale (NRS) score**

The NRS score is a numeric scale in which individuals rate pain from 0 (no pain) tot 10 (worst pain). This is a subjective score which is assessed verbally and used frequently in standard clinical care in multiple medical specialties.

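### Section 7.2 rules out blinding for every role on a reason that does not reach the 6-week caller or the analyst, so these avoidable sources of bias stay in

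*Combined protocol and SAP*

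**What the plan says.** Section 7.2 states "Blinding however, is not possible in this study as usage of the medical device is clear" and draws no distinction between roles. The same section says of allocation "This randomization will be performed postoperatively by the research team".

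Section 7.1.1 names four main parameters: the NRS, the QoR-15, the STAI-6 and analgesic use. The first three are reported by the patient. On collection, the protocol gives only this:

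- NRS (section 7.3): "This is a subjective score which is assessed verbally".
- Days 1 to 3 (section 7.3): scores are taken after each of the two daily sessions, and for controls "Outcomes will be measured at the same aforementioned moments in the control group".
- Six weeks (section 7.3): "At follow-up, participants will be called to gather one-time QoR-15 and STAI-6 questionnaire data 6 weeks after the surgery".

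Section 9.1 compares the groups on days 1, 2 and 3 and on mean values over them. It does not list 6 weeks and does not mention a masked analysis. Section 11.1 stores data under code numbers, but these identify patients and do not conceal arms.

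**The concern.** A visible device is a reason why some people cannot be masked, and the plan treats it as a reason to mask nobody. The people left unmasked include some who could be kept unaware of the arm. Nothing bars the research team that randomises from also asking for the scores, making the 6-week calls and running the analysis.

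At stake is whether a difference in subjective scores can be read as an effect of the device. A questioner who knows the arm can influence an answer given aloud. An analyst who knows the arm can be swayed in choices the plan leaves open. Either influence would be inseparable from a device effect once the data are in. Patient expectation is a further source, and masking staff does not remove it.

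**Working it through.** **Step 1. Test the stated reason role by role.**

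| Role | Does visible device use prevent masking? | What the protocol provides |
|---|---|---|
| Patient | Yes | Unblinded |
| Staff present at a session | Yes | Unblinded |
| Person asking the NRS | Only if present at, or told of, the session | Asked verbally; person not named |
| Person handling QoR-15 and STAI-6, days 1 to 3 | As above | Neither person nor mode of completion stated |
| Caller at 6 weeks | No: sessions end on day 3, so the call comes about 42 − 3 = 39 days later | Phone; caller not named or masked |
| Analyst | No | Not mentioned |

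The reason holds for the first two rows and fails for the last two. For the middle two, the answer depends on facts the protocol does not give.

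**Step 2. Reproduce the plan's own figure.** Section 4.4 gives 92.7% power for a two-sided Wilcoxon-Mann-Whitney test at 0.05 with n = 50 per group. X is Table 1 Group 1 (mean 4.77) and Y is Group 2 (mean 3.55), a difference of about 1.2 points.

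- p = P(X<Y) + ½P(X=Y) = 0.2395 + ½ × 0.1439 = 0.3115 (Table 1: 0.311).
- Null SE = √[C(2n+1)/(12n²)], where C = 1 − Σm³ and m is the average of the two proportions in each category. C = 0.9644, so SE = √(0.9644 × 101/30,000) = 0.0570.
- Alternative SE = √{[E(A²) − p²]/n + [E(B²) − p²]/n}, where A = P(Y>x) + ½P(Y=x) over X, and B = P(X<y) + ½P(X=y) over Y. This gives 0.0521.
- Power = Φ[(0.1885 − 1.96 × 0.0570)/0.0521] = Φ(1.47) = 93.0%.

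Simulation of 20,000 trials gives 92.9%. The stated power reproduces, and this point does not affect it.

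**Step 3. Illustrate how sensitive the NRS test is to a reporting shift.** Assumptions, none from the documents: no true effect; both arms follow Table 1 Group 1; a share f of VR patients is recorded 1 point lower (a score of 1 becomes 0); one test at 0.05.

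With f = 1, p = 0.3537, and p is linear in f, so p = 0.5 − 0.1463f. The rejection probability is the sum of both tails, with standard errors as in step 2. For f = 20%, p = 0.4707, and the tails are Φ[(0.0293 − 1.96 × 0.0569)/0.0565] = 7.3% and 0.6%, in total 7.9%.

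| f | p | Formula | Simulation (40,000 trials) |
|---|---|---|---|
| 0% | 0.500 | 4.9% | 5.0% |
| 20% | 0.471 | 7.9% | 7.9% |
| 30% | 0.456 | 11.8% | 12.1% |
| 50% | 0.427 | 24.5% | 24.7% |

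**Step 4. What step 3 can support.** It shows that a shift well below the planned 1.2 points would inflate false positives. It does not show that a shift occurs, in which direction, or from which source. The same model describes an interviewer's influence and a patient's own expectation.

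**The case against.** The strongest reply is that the main bias survives any fix. All three scores are given by patients who know their arm, and the documents contain nothing that sizes the interviewer's part. That stands, and it limits the benefit.

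Several stronger readings are tempting, and the documents do not support them:

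- A reader might infer that the person who has just run a VR session asks for the score. The protocol does not say who runs sessions or who collects scores. The measurement times are matched in controls.
- A reader might infer that interviewer influence reaches all three scores throughout. Verbal collection is stated only for the NRS, and phone collection only for 6 weeks. The QoR-15 and STAI-6 may already be self-completed on days 1 to 3; influence there is possible but not shown.
- A reader might treat the 6-week result as the main loss. Section 9.1 does not list 6 weeks as a comparison, so masking the caller protects none of the comparisons it does list.
- A reader might see a risk in the manufacturer's sponsorship. Section 11.5 describes device supply and unrestricted publication, section 11.1 limits data access to the research team, and section 11.6 assigns monitoring to the hospital's own centre. No role in collection or analysis is given to the manufacturer.

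Cost is also a fair objection. The protocol gives no staffing, and the research team itself randomises, so a caller without access to the allocation may not be available. This is why that step should be conditional. It does not weaken the case for arm-coded analysis or patient-marked scores, which need no additional person.

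**Conclusion.** The point holds in a limited form. Section 7.2 gives up masking for every role, but its reason covers only patients and staff who see the device in use. The 6-week caller and the analyst fall outside that reason and are masked nowhere else, and the collector of the scores is unspecified.

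The size of the resulting bias cannot be derived from the documents. The rejection rates of about 8%, 12% and 24 to 25% rest on an assumed 1-point shift in 20%, 30% or 50% of VR patients in a single NRS test. They are not an estimate of what masking would remove. Sample size, alpha and power are unaffected. This is a cheap improvement of lower priority, not a flaw that undermines the trial.

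**What to change.** Limit the statement in section 7.2 to patients and ward staff, state who collects each score, and add:

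1. In both arms the patient marks the NRS, QoR-15 and STAI-6 on a form or tablet. A fixed verbal script is used only when the patient cannot do so, and its use is flagged in the data.
2. The between-group analysis is run with arms coded A and B until results are final.
3. Where the existing team allows, the 6-week call is made by a member without access to that patient's allocation, who asks the patient not to mention VR and records any unmasking.

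Items 1 and 2 protect the day 1 to 3 comparisons; item 3 protects only the 6-week data. State as limitations that patients remain unblinded, that their expectation can still affect all three scores, and that analgesic use is not protected by these steps.

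The cost is protocol wording and task allocation, with no added visit. The downsides are some scheduling effort, occasional unmasking on the phone, and a few scripted verbal answers that mix collection modes within an outcome.

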### **7.3 Study procedures**

The study will consist of 100 participants who have undergone an uncomplicated surgical CABG procedure.

The intervention group includes 50 patients using a VR distraction therapy device with 3D interactive nature environments in the post-operative stage for pain and anxiety management. The control group includes 50 patients who will be treated with conventional post-operative pain and anxiety management.

The intervention group will test-use the VR distraction therapy device on the day of clinical admission prior to surgery and use it therapeutic at day 1, 2 and 3 after surgery on the general ward.

Daily usage of the VR distraction therapy device consists of two sessions each day (morning and afternoon) with a duration of 20 minutes per session. The specific virtual environment for each session will be selected freely by the participants.

Outcomes will be measured daily, at the end of each session, which is done 1) after the doctor's ward visit in the morning and 2) after the shift change of the nurse team.

Outcomes will be measured at the same aforementioned moments in the control group.

Outcomes will be measured by using the Numeric Rating Scale (NRS) to assess the effect of pain on mobility, Quality of Recovery-15 questionnaire, State-Trait Anxiety Inventory-6 questionnaire and assessment of analgesic use.

At follow-up, participants will be called to gather one-time QoR-15 and STAI-6 questionnaire data 6 weeks after the surgery.

#### **Numeric Rating Scale (NRS) score**

The NRS score is a numeric scale in which individuals rate pain from 0 (no pain) tot 10 (worst pain). This is a subjective score which is assessed verbally and used frequently in standard clinical care in multiple medical specialties.

#### **Quality of Recovery-15 (QoR-15) questionnaire**

The QoR-15 questionnaire is a clinical validated instrument to measure post-operative quality of recovery.

#### **State-Trait Anxiety Inventory-6 questionnaire**

The STAI-6 questionnaire is a validated psychological inventory designed to measure worry, tension and anxiety in an individual.

### **7.4 Withdrawal of individual subjects**

Subjects can leave the study at any time for any reason if they wish to do so without any consequences. The investigator can decide to withdraw a subject from the study for urgent medical reasons.

### **7.5 Replacement of individual subjects after withdrawal**

Upon withdrawal of a subject, the data collected will not be used for the study and will be deleted.

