#### **7.6 Follow-up of subjects withdrawn from treatment**

Not applicable.

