## 9. STATISTICAL ANALYSIS

### 9.1 Primary study parameters

The included data (NRS score, STAI-6 score, QoR-15 score) will be presented as mean  $\pm$  standard deviation. Ratios will be given for statistical assessment of non-continuous variables (assessment of analgesic use). Because the data is expected to be non-normally distributed, Wilcoxon (Mann-Whitney) Rank-Sum testing will be performed to analyze differences between groups. Differences between groups will be assessed for each measurement at each point in the study (day 1, 2 and 3) and cumulative as mean values. SPSS 26.0 (SPSS Inc, Chicago, IL) for Windows is used to assess statistical analyses.

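### Section 7.5 deletes the data of every withdrawn patient and section 9.1 defines no analysis set or missing-data method, so an unblinded randomised comparison loses patients after allocation

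*Combined protocol and SAP*

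**What the plan says.** Section 7.5 of the protocol: "Upon withdrawal of a subject, the data collected will not be used for the study and will be deleted". Section 7.4 sets out whom this reaches. Patients may go of their own accord ("Subjects can leave the study at any time for any reason if they wish to do so without any consequences"), and there is also a second route: "The investigator can decide to withdraw a subject from the study for urgent medical reasons". Section 7.6, on follow-up of subjects withdrawn from treatment, reads only "Not applicable".

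Section 9.1 gives summary statistics, rank-sum tests at days 1, 2 and 3 and on mean values, and the software. It contains no analysis set, missing-data method or sensitivity analysis. Section 4.4 has no dropout allowance.

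Section 7.2 places randomisation "directly after the patient returns to the clinical ward after surgery", before the therapeutic VR sessions, and says "Blinding however, is not possible in this study as usage of the medical device is clear".

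Other passages bear on who stays in:

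- Section 6.3, on device symptoms: "participants in this study will be excluded from further participation as soon as the above mentioned symptoms are noticed". Section 12.1(e) repeats this.
- Section 12.1(j) speaks only of switching the device off and treating the symptoms.
- Section 7.7 says patients with eye fatigue, nausea or disorientation are not included, which may be only an entry screen.
- Section 4.3 lists readmission to intensive care as an exclusion criterion.

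**The concern.** Randomisation protects the comparison only if the patients analysed are those who were randomised. Under 7.4 and 7.5 a patient withdrawn on day 3 loses valid day 1 and day 2 scores, even if that patient never objected to their use. Because patients and staff know the allocation, reasons for leaving can differ between arms and be related to pain, anxiety or recovery. The result could then favour or disfavour VR without any true effect.

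Two further routes are conditional, because no sentence says they count as withdrawal under 7.5:

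- **Device symptoms (6.3, 12.1(e)).** Symptoms caused by the device arise only where it is used. Even if data already collected were kept, ending participation would lose later outcomes, up to day 3 and week 6, mainly in the VR arm.
- **Intensive care readmission (4.3).** With randomisation on return to the ward, a readmission would normally follow randomisation, in either arm.

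A missing analysis set can still be written before the data are analysed. Deleted data cannot be recovered, and no sensitivity analysis can use them.

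**Working it through.** **Inputs.** From section 4.4 and Table 1: 50 per group, two-sided alpha 0.05, stated power 92.7%, P(X<Y) = 0.311, and the proportions for NRS 1 to 8. Table 1 does not label its arms; Group 1 is taken as conventional care and Group 2 as VR. Removal rates and their link with pain are assumptions.

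**Step 1: the plan's own figure.** P(X<Y) plus half the probability of a tie is 0.2395 + 0.5 × 0.144 = 0.3115 (plan: 0.311). With v0 the tie-corrected null variance and v1 the variance under the alternative, power = Φ[(|p − 0.5| − 1.96√v0)/√v1] = 92.9%. Simulation gives 92.6-92.8%. The stated 92.7% is reproduced, and it requires all 100 patients to be analysed.

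**Step 2: Table 1 means.**

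- Group 1: 0.059 + 0.118 + 0.264 + 1.312 + 0.595 + 0.882 + 0.420 + 1.120 = 4.770.
- Group 2: 0.050 + 0.604 + 0.540 + 1.000 + 0.250 + 0.540 + 0.420 + 0.144 = 3.548.
- Difference: 1.222. This is derived from Table 1; section 4.4 does not state it.

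**Step 3: error when VR has no effect.** Both arms follow Group 1, 50 are randomised per arm, the removal probability is logistic in NRS, and the test is a tie-corrected two-sided Mann-Whitney test (1,000,000 runs per setting). For removal in one arm, bias = removal rate × (mean of removed − mean of kept). For example, 0.20 × 1.69 = 0.338.

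Removal in the VR arm only, higher-pain patients more likely to go:

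| Removed | Weaker link (slope 0.25; removed about 0.9 points higher): bias / type I error | Stronger link (slope 0.5; removed about 1.7 points higher): bias / type I error |
|---|---|---|
| 5% | 0.046 / 5.14% | 0.086 / 5.45% |
| 10% | 0.092 / 5.52% | 0.172 / 6.94% |
| 20% | 0.183 / 7.07% | 0.338 / 12.45% |
| 30% | 0.272 / 9.45% | 0.496 / 20.53% |

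Other patterns, stronger link:

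- Control removed at half the VR rate, same link: 20% vs 10% gives 0.166 / 6.69%; 30% vs 15% gives 0.241 / 8.46%.
- Equal rates, linked to pain in VR only: 20% gives 0.338 / 11.74%; 30% gives 0.496 / 18.30%.
- Equal rates and equal links, or removal unrelated to pain: no bias, error 4.9-5.0%.
- Lower-pain VR patients removed: the bias turns against VR, 0.083 at 5%, 0.320 at 20% and 0.475 at 30%.

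**Step 4: what remains after deletion.** If exit counts by arm are kept, only bounding is possible. Suppose the kept patients show means of 4.770 and 3.548, and the deleted VR scores could all be 10 or all be 0.

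- 5 of 50 deleted: the VR mean is (45 × 3.548 + 50)/50 = 4.193 or (45 × 3.548)/50 = 3.193, so the all-randomised difference lies between 0.58 and 1.58.
- 10 of 50 deleted: the VR mean is (40 × 3.548 + 100)/50 = 4.838 or (40 × 3.548)/50 = 2.838, so the difference lies between −0.07 and 1.93.

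**Step 5: power.** 50 vs 45 gives 91.4%, 50 vs 40 gives 89.5%, and 40 vs 40 gives 86.1%. Loss of power is secondary; bias is the main issue.

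**The case against.** The strongest reply concerns size. Only voluntary and urgent medical withdrawal certainly trigger 7.5, and both can occur in either arm. Removal confined to VR comes mainly from the device-symptom text, whose connection to 7.5 is not stated. With withdrawal in both arms at unequal rates the inflation is smaller: 6.69% at 20% vs 10% with the stronger link, and about 5.6% with the weaker one. Therapeutic use and in-hospital outcomes span only three days, so losses may be few, and at 5% removal the effect is close to negligible. All of this stands, and it limits what can be claimed about magnitude.

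The bounds in step 4 are extremes: no pilot patient scored 0, 9 or 10. The allocation of Table 1's groups to arms is an assumption. These points also stand, but they affect the illustration and not the rule.

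Section 7.5 may reflect a promise made to participants. The consent text is not available here, so retention can be recommended only as far as consent permits. That does not explain deleting data from someone the investigator withdraws and who has not asked for deletion.

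The intensive care criterion may be meant only for eligibility before randomisation. The text leaves this open, so it is a point to reconcile and not part of the core finding.

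**Conclusion.** The concern holds, and the plan must be changed on this point. Sections 7.4 and 7.5 as written remove randomised patients from the comparison, and nothing in 7.6, 9.1 or elsewhere repairs it. That conclusion comes from the text and needs no assumption about rates.

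The numerical impact cannot be derived from the documents. For a single NRS measurement, which is one of four main parameters, the assumed scenarios range from no bias to a spurious difference of about 0.5 points with a type I error of about 20%. Direction depends on who leaves. Equal numbers lost per arm would not be reassuring by themselves. The priority rests on the deletion being irreversible, on the open-label design with mostly patient-reported outcomes, and on the low cost of correction.

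**What to change.** 1. **Section 7.5:** keep and analyse data already collected unless the participant asks for deletion, as the consent allows.
2. **Sections 7.5 and 7.6:** separate stopping the device from leaving the study. For those who stop the device but do not withdraw, continue NRS, QoR-15, STAI-6 and analgesic use through day 3, and QoR-15 and STAI-6 at week 6.
3. **Section 9.1:** make the primary analysis all randomised participants in their allocated arm. State how a missing score enters the rank-sum test and the cumulative mean, add a missing-data sensitivity analysis, and report device discontinuations and withdrawals by arm with reasons.
4. **Reconcile** 6.3, 12.1(e), 12.1(j), 7.7 and the readmission criterion in 4.3 with this text, so that none removes a randomised participant from the analysis. When the device is stopped is for the sponsor to decide.

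Two smaller points can be settled in the same amendment. Sections 3 and 7.3 have the intervention group test the device before surgery, although 7.2 randomises afterwards. It is also unclear whether deletion under 7.5 covers the adverse-event records that 8.2.1 requires.

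**Cost:** a protocol amendment, plausibly substantial under 11.2 because it affects scientific value, revised patient information, and a few more bedside and telephone questionnaires. The estimated effect may be smaller, because patients who stop the device are counted.
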